2.0 INTRODUCTION

Total Knee Replacement (TKR) has evolved to a point where implant design combined with instrumentation and surgeon skill results in excellent implant survival. The New Zealand National Joint Register reported over 6000 knee replacements performed in New Zealand in 2009, with annual figures increasing over the last 10 years.

Total Knee Replacements are undertaken to treat a range of conditions including osteoarthritis, rheumatoid arthritis, avascular necrosis and secondary arthritis resulting from trauma.

Current surgical techniques make use of generic, re-usable instrumentation, consisting of intra- and/or extra-medullary rods on the femur and tibia to determine alignment in relation to anatomical landmarks, combined with bone resection guides

which ultimately determine position and orientation of the definitive implant components.

Traditionally, the goal of TKR has been to position the components such that the post-operative alignment goal is a straight limb, or a mechanical axis of 0° (Insall & Scott, 2001). The mechanical axis is defined by lines joining the centre of the femoral head, centre of the knee joint and the centre of the ankle. Despite the best efforts of the surgeon, the resulting limb alignment varies away from 0° by a small amount (typically less than ±3° in 80% of cases).

More recently, the use of computer navigation systems has been introduced to surgical practice with the aim of improving the ability to obtain post-operative limb alignment as close as possible to 0° (Chauhan et al, 2004).

Whilst achievement of neutral limb alignment has been considered desirable from an engineering point-of-view – to maximize implant longevity through minimizing the deleterious effects of polyethylene insert wear and particle-induced osteolysis and implant loosening – patient satisfaction of TKR has not always been ideal. Despite surgery being performed technically correct by surgeons, up to 1 in 5 patients express dissatisfaction in the functional result (Bourne et al, 2009). Patient expectations after surgery are also increasing due in part to the adoption of more active lifestyles amongst total knee replacement recipients where return to function can be of primary importance.

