3.0 OBJECTIVES

The primary objective of this study is:

• To demonstrate, through calculation of Oxford Knee Score at 12 months postoperative, that total knee replacement (TKR) performed using the ShapeMatch® Cutting Guide provides improvement from preoperative levels of patient pain and function comparable to the improvement obtained with TKR performed using computer-assisted Navigation. Oxford Knee Scores will be calculated pre-operatively and at 6 weeks, 6 months and 12 months post-operatively.

The secondary objectives of this study are:

- The efficacy objective is to compare radiographic, pain, function and health-related quality of life (QOL) between the ShapeMatch® Cutting Guide group and the computer-assisted Navigation control group. This objective will be achieved by utilizing the following instruments pre-operatively and at the 6-week, 6-month and 12 month visits:
 - Perth CT protocol
 - AP and ML X-rays
 - Oxford Knee Score
 - The International Knee Society Score (IKSS)

- The Forgotten Joint Score (FJS-12)
- WOMAC
- EQ-5D-3L
- VAS Pain
- To compare the cost-effectiveness and cost-utility of the procedure between the ShapeMatch[®] Cutting Guide group and the computer-assisted Navigation control group. This objective will be assessed by recording and calculating the following parameters:
 - o Wound length
 - Total duration of operating procedure (anaesthetic time and skinto-skin incision time)
 - o Cost of consumable items used during operating procedure
 - Length of stay in hospital
 - o Quality-adjusted life-years (QALYs) from EQ-5D-3L

The hypothesis is that there is a statistically significant improvement in functional outcome 12 months following a primary Total Knee Replacement when kinematic limb alignment (using ShapeMatch® Cutting Guide) is used compared to that resulting from a goal of neutral mechanical axis alignment (using computer-assisted Navigation).

The Extension Study Primary Objective is:

To determine the clinical and radiographic outcomes at 2 years and 5 years post-surgery, in patients receiving a Stryker Triathlon[®] Total Knee System for Total Knee Arthroplasty (TKA) implanted using either Stryker OtisMed[®] ShapeMatch[®] Technology (intervention) or Stryker PrecisioN v4.0 Knee Navigation (control).

The Extension Study Secondary Objectives are:

 To determine the revision rate, device-related adverse events and reoperation rates.

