12.2 Data Capture and Analysis

All data will be recorded on 2-part NCR paper Case Report Forms (CRFs). The surgeon will complete and sign forms at the time of completion. Original CRFs will be collected by Stryker for data entry. Copies will remain at the Investigator site. Archiving will be undertaken in accordance with ICH/GCP guidelines (Appendix 6).

Any unclear or ambiguous data will be queried and all cleaned data will be entered into a database for tracking purposes.

The primary outcome data gathered from patients in each study group will be pooled and summarized.

For the primary objective of the study, the 95% confidence interval of the difference in total Oxford Knee Score improvement (at 12 months post-operative) between the Intervention Group and the Control Group will be computed. Two and five year data will be analysed as per the 12 month data.

For secondary objectives, independent two-sample t-test or Wilcoxon non-parametric rank-sum test will be used to compare the International Knee Society Score (IKSS), Forgotten Joint Score (FJS), WOMAC, EQ-5D and VAS Pain scores between the Intervention Group and the Control Group at all available visits. Please note that the test we intend on using will be dependent on the distribution of the data collected following appropriate normality testing. Adjustments will be made for multiple testing at each level.

Independent two-sample t-test or Wilcoxon non-parametric rank-sum test will also be used to compare cost-effectiveness and cost-utility between the Intervention Group and the Control Group. As mentioned above, this will also be dependent on the distribution of the data collected.

Adverse events will be tabulated separately and reviewed for any commonalities. Revision surgery data from the Extension Study will be compared to the revision rates reported in the National Joint Registry report at 2 years and 5 years. A cost benefit analysis will be undertaken with the use of data from the Australian Government Hospital Casemix Protocol Annual Report.

A formal interim analysis will take place following completion of the ShapeNZRCT-10 study (12 month visit). Additionally, formal interim analyses will take place following all participants' completion of the 2 year visit and again following completion of all participants' 5 year follow-up visits.

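### Section 12.2 plans no between-arm comparison of adverse events, adverse device events, re-operations or revisions; the only stated comparator for revisions is an external registry

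*Combined protocol and SAP*

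**What the plan says.** Section 12.2 names a between-arm analysis for each of these:

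- Oxford Knee Score: "the 95% confidence interval of the difference in total Oxford Knee Score improvement (at 12 months post-operative) between the Intervention Group and the Control Group".
- Secondary scores, by t-test or rank-sum test: the IKSS and "Forgotten Joint Score (FJS), WOMAC, EQ-5D and VAS Pain scores between the Intervention Group and the Control Group at all available visits".
- Cost-effectiveness and cost-utility, by the same tests.

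Safety has two sentences there. The first is "Adverse events will be tabulated separately and reviewed for any commonalities". The second is "Revision surgery data from the Extension Study will be compared to the revision rates reported in the National Joint Registry report", at 2 and 5 years. The matching extension objective in section 3.0 is "To determine the revision rate, device-related adverse events and reoperation rates", which is to determine the rates and not to compare them.

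Sections 19 and 21 cover the reporting of single events and site monitoring, and section 15.0 has data monitored for trends. None of them sets one arm against the other. Section 12.2 also announces formal analyses after the 12-month, 2-year and 5-year visits, without giving them any safety content.

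**The concern.** Section 2.0 explains that surgeons aim for neutral alignment "to maximize implant longevity through minimizing the deleterious effects of polyethylene insert wear and particle-induced osteolysis and implant loosening". The intervention aims for a different alignment by design. Sections 7.0 and 8.1 give both arms the same Triathlon components, so randomisation isolates the alignment and instrumentation strategy. That makes the control arm the natural reference for revision, re-operation and device-related events.

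A comparison with the registry answers another question: whether trial patients fare like registry patients. It is non-randomised, and it says nothing about navigation in the same hospitals and with the same surgeons. At stake is the trial's only randomised evidence on harm, which has no prespecified analysis. The primary Oxford Knee Score result is not affected.

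**Working it through.** **1. The plan's own figure.** The only sample size calculation is for the Oxford Knee Score (section 12.1): difference 42 − 37 = 5, SD 8.30, 80% power, 5% significance (two-sided assumed).

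n per arm = 2(1.960 + 0.842)² × 8.30² / 5² = 15.70 × 68.89 / 25 = 43.3, so 44. With the t distribution, power is 0.798 at 44 and 0.807 at 45, so 45. Allowing 10% loss, 45 / 0.90 = 50. The stated figures reproduce. No safety outcome has a rate or a calculation anywhere in the documents.

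**2. Outcomes against stated comparators.**

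| Outcome | Stated comparator |
|---|---|
| Oxford Knee Score, IKSS, FJS, WOMAC, EQ-5D, VAS Pain, cost | Other arm |
| Radiographs | Other arm (objective in 3.0; no method in 12.2) |
| Adverse events | None; tabulated, reviewed for commonalities |
| Adverse device events, re-operations | None |
| Revisions | External registry |

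The sentence that carries the 12-month analysis forward to 2 and 5 years follows the Oxford Knee Score sentence. The 12-month plan contains no between-arm safety analysis to carry forward.

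**3. What pooling would do, if it were done.** Let the registry rate be r, the control rate r and the ShapeMatch rate r + e. With equal arms the pooled rate is (r + r + e)/2 = r + e/2, so the excess is halved.

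The documents give no rates, so those below are assumptions: ShapeMatch at three times the registry rate, control at the registry rate. The registry comparisons use an exact one-sided binomial test at 0.025, treating the registry rate as fixed. The between-arm test is Fisher's exact test, two-sided at 0.05, counting only results with the excess in ShapeMatch.

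| Registry / ShapeMatch | Pooled 100 vs registry (events needed) | ShapeMatch 50 vs registry (events needed) | Fisher, 50 vs 50 |
|---|---|---|---|
| 2% / 6% | 21% (6) | 35% (4) | 3% |
| 3% / 9% | 25% (8) | 47% (5) | 9% |
| 5% / 15% | 42% (11) | 64% (7) | 24% |

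Two things follow. Analysing the ShapeMatch arm separately recovers what pooling loses. A between-arm test has the least power of the three, so the case for the randomised contrast is that it answers the right question without case-mix bias, not that it detects more.

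**4. Precision of a risk difference.** Take, for illustration, 5/50 against 1/50, a difference of 0.10 − 0.02 = 0.08. The Wilson limits are 0.0435 to 0.2136 and 0.0035 to 0.1050. Newcombe's interval is:

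- lower: 0.08 − √[(0.10 − 0.0435)² + (0.1050 − 0.02)²] = −0.022
- upper: 0.08 + √[(0.2136 − 0.10)² + (0.02 − 0.0035)²] = 0.195

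An interval from −2 to +19 percentage points is wide, but it states plainly what the trial can and cannot exclude.

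**5. Denominators after 12 months.** Section 6.4 keeps patients already revised out of the extension, and section 10.0 requires a second consent. Section 17.2 lists re-operation as ending participation, and section 17.3 does the same for unblinding. The registry comparison uses revision data from the extension only, so revisions before extension entry may fall outside it. A patient who leaves after a re-operation and is revised later would not be observed.

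**The case against.** **The table may already be by arm.** This is a fair reading of the first safety sentence, and if it is right, part of the remedy is already intended. The ambiguity remains, though, and a review for what events have in common is not a search for a difference between arms.

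**Some safety-relevant outcomes are compared.** The objective "The efficacy objective is to compare radiographic, pain, function and health-related quality of life (QOL) between the ShapeMatch" group and the navigation group covers X-rays, which section 11.0 says are taken to assess implant stability. The IKSS includes stability and deformity and is tested between arms. So a reader should not infer that nothing bearing on safety is compared. The gap is confined to adverse events, adverse device events, re-operations and revisions.

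**Pooling is not stated.** A reader might infer that the plan combines the arms against the registry. The text does not say so. Where section 12.2 speaks of pooling, it concerns primary outcome data in each study group. The dilution in step 3 is conditional.

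**The registry might be thought a higher-risk population that would mask harm.** The entry criteria make this conceivable, but the documents give neither the registry's case mix nor its revision rate. The remark in section 12.1 about mostly conventional instruments describes a 6-month Oxford score, not revision rates.

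**A between-arm test would miss most excesses.** This stands, as step 3 shows. It rules out a powered test as the remedy, but not an estimate with its interval.

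**Other safeguards exist.** Sections 15.0 and 19.2 provide monitoring for trends, 24-hour reporting of serious events and evaluation of device effects. They work event by event and do not supply the arm-level comparison.

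**Conclusion.** The point holds as a gap in the planned analysis. For four kinds of harm the randomised control is not used, and for revisions a non-randomised comparator is specified in its place. The plan should be changed, but the defect does not threaten the primary result.

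The certain part is textual: no section plans these comparisons. The size is conditional. If the arms are pooled, an excess in one arm is halved, and for a tripled rate from an assumed 2–5% the chance of flagging it falls from 35–64% (ShapeMatch alone) to 21–42% (pooled). These figures assume 50 followed per arm, a control rate equal to the registry rate, and a registry rate known without error.

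The documents do not support the conclusion that a harm would be missed under this plan and caught by a between-arm test: the power of such a test is about 3–24% in the same scenarios.

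**What to change.** In section 12.2:

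1. State that adverse events, serious adverse events, adverse device events, re-operations and revisions are tabulated by randomised arm, as patients with at least one event.
2. Report the risk difference with an exact or Newcombe 95% confidence interval at 12 months, on all randomised and operated patients.
3. Report the same at 2 and 5 years with the denominator stated for each arm, counting revisions and re-operations recorded before extension entry, and list by arm how many patients did not enter or left, and why.
4. Make the registry comparison separately for each arm, as description.
5. Say that these are descriptive estimates and not powered tests.

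The cost is a few sentences and one table. The 12-month table uses data already collected. The later estimates will be limited by who enters and stays in the extension; a changed table cannot restore the full randomised denominators, and the report should say so.

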5.0 LENGTH OF STUDY AND PATIENT PARTICIPATION

The enrolment period is expected to be 6 months or until the required sample size is reached. Participants in both the Control Group and Intervention Group will be followed for 12 months post-surgery. It is anticipated that the entire study will take approximately 18 months to complete, excluding data analysis.

Following the 12 month follow-up visit, patients will receive an invite to continue participation in the study via enrollment into the Extension Study. Patients will need to meet the inclusion and exclusion criteria for the study (see sections 6.3 and 6.4) and provide informed consent in order to participate.

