6.2 Exclusion Criteria

- The patient has a history of total, unicompartmental reconstruction or fusion of the affected joint.
- Patient has had a previous osteotomy around the knee.
- The patient is morbidly obese (BMI ≥ 40).
- The patient has a deformity which will require the use of stems, wedges or augments in conjunction with the Triathlon Total Knee System.
- The patient has a varus/valgus malalignment ≥ 15° (relative to mechanical axis).
- The patient has a fixed flexion deformity ≥ 15°.
- The patient has a neuromuscular or neurosensory deficiency, which would limit the ability to assess the performance of the device.
- The patient has a systemic or metabolic disorder leading to progressive bone deterioration.
- The patient is immunologically suppressed or receiving steroids in excess of normal physiological requirements.
- Patient has a cognitive impairment, an intellectual disability or a mental illness.
- The patient is pregnant.
- The patient has metal hardware present in the region of the hip, knee or ankle (as this is known to create geometrical distortion in the region of the implant).
- The patient has any known contraindications for undergoing assessment by MRI (e.g. ferrous implants, metallic clips, magnetically activated implanted devices such as cardiac pacemakers, etc.).

6.3 Extension Study: Inclusion Criteria (applicable to patients electing to continue participation in the Extension Study)

- Patient was enrolled in ShapeNZRCT-10 and completed either the 6 month or 12 month follow-up visit (or both).
- Patient is willing and able to give informed consent to participate in the study.
- Patient is willing and able to comply with the specified clinical and radiographic evaluations.

6.4Extension Study: Exclusion Criteria (applicable to patients electing to continue participation in the Extension Study)

- Patient no longer has the Triathlon[®] Total Knee System in situ, including patients that have had revision surgery.
- Patient has a cognitive impairment, an intellectual disability or a mental illness that is considered by the investigator to inhibit the patient's capacity to consent to research and the ability to participate in it.
- Patient no longer resides in a geographical location that would reasonably permit clinic visits at protocol specified intervals.

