Medical History Review: For participants continuing on in the extension study, details of any significant medical events that occur from the end of the 12 month study period to the signing of the extension study consent form will be captured as medical history in the extension study. This will ensure no adverse event data will be missed between termination from the ShapeNZRCT-10 study and re-enrolment into the Extension study.

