17.2 Withdrawal from Study

Participants will be advised that they may voluntarily withdraw from the study at any time, for any reason and they are not obligated to reveal the reason to the Investigator and it will not affect their medical care. However, in such cases, appropriate effort will be made to determine the reason for withdrawal from the study. The Investigator may request a letter from the patient noting his or her desire to withdraw from the study. All attempts to locate participants lost to follow up will also be documented.

Participants will be informed that should they withdraw from the study they should remain under the care of an appropriately experienced physician until the physician deems further follow-up unnecessary.

The following are circumstances for which a patient would be identified as not continuing their participation in the study:

- Study Completed / Terminated
- Death
- Unable to Return
- Unwilling to Return
- Concurrent Illness
- Lost to follow-up
- Re-operation of the affected knee joint, including revision of total knee replacement components
- Other

Additionally, the patient may be withdrawn by the Investigator, if he/she is unable to continue participation in the study due to some condition unrelated to this study.

A Study Completion Form will be completed for all participants who withdraw from the study.

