19.2 Reporting of Events

Adverse Events:

Any adverse event that occurs at any time point from the beginning of the surgical procedure until either the patient is terminated from the study, or 30 days post-completion, should be recorded as follows:

All information on general medical, operative and device related complications (adverse events) will be documented on Case Report Forms (CRFs). Information should include date of occurrence, description, severity, relationship to study device, treatment and date of resolution.

The Investigator must determine if the event is related to the device. Any adverse event in a study patient must be monitored until the event is resolved or considered non-clinically significant by the Investigator.

Expected Events: Should be reported to the Sponsor soon as possible, but not later than ten working days after the Investigator first learns of the effect.

Adverse Device Events

Should any adverse device events occur, the study staff will ensure that these are documented by the Investigator and reported immediately to the Sponsor. They should also be reported to the reviewing Ethics Committee and Institution as soon as possible, but not later than fifteen working days after the Investigator first learns of the effect, unless an earlier timeline is specified by individual study sites. The Investigator with the Sponsor will conduct an evaluation of such effects. Following this evaluation, if the Investigator determines that an unanticipated adverse device effect presents an unreasonable risk to participants, the Investigation will be terminated as soon as possible. Termination shall occur no later than five working days after the Investigator makes this determination and no later than fifteen working days after the Investigator first receives notice of the unanticipated adverse effect.

Serious Adverse Events:

Any adverse event that is considered to be of serious nature and occurs at any time point from the signing of Informed Consent Form until either the patient is terminated from the study, or 30 days post-completion, should be recorded as follows:

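### The 2- and 5-year registry comparison in 12.2 draws on Extension Study revisions, so revisions before Extension entry drop out; if the registry rate runs from surgery, the trial rate is biased low (minor)

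*Combined protocol and SAP*

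**What the plan says.** Section 3.0 makes the revision rate a secondary objective of the Extension Study. Section 12.2 gives the analysis: "Revision surgery data from the Extension Study will be compared to the revision rates reported in the National Joint Registry report", at 2 and 5 years. It does not state the registry metric, the time origin, the denominator, a test or a decision rule.

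Entry to the Extension is set out elsewhere:

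- Section 5.0: "Following the 12 month follow-up visit, patients will receive an invite to continue participation in the study via enrollment into the Extension Study".
- Section 6.3 admits patients who attended the 6-month visit, the 12-month visit, or both.
- Section 6.4 excludes patients who no longer have the "Total Knee System in situ, including patients that have had revision surgery".
- Section 17.2 lists, among the reasons for not continuing in the study, "Re-operation of the affected knee joint, including revision of total knee replacement components".

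Revisions during the main study are nevertheless recorded. Section 19.2 requires adverse events to be documented on CRFs "from the beginning of the surgical procedure until either the patient is terminated from the study, or 30 days post-completion". Section 17.2 adds: "A Study Completion Form will be completed for all participants who withdraw from the study". Section 11.0 (Medical History Review) collects events between the end of the 12-month study and Extension consent, but only "For participants continuing on in the extension study".

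**The concern.** The Extension cohort is unrevised at entry by construction. A revision rate computed from it describes what happens after entry to knees that have already survived to that point. Registry rates at 2 and 5 years may instead count every revision since surgery. Set side by side without adjustment, the two figures would have different time origins, and the trial figure would look more favourable than the same trial counted from surgery. A confidence interval shows imprecision but does not reveal a mismatched time origin, so a reader of the final report could not see the problem from the numbers.

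**Working it through.** The plan gives no revision rate, expected count or precision for this comparison, so there is no figure of its own to reproduce. The direction follows from the text plus two assumptions. The size is illustration only.

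**Inputs from the documents.** Source of revisions: Extension Study (12.2). Entry: after the 12-month visit (5.0), whose window is ±2 months (1.0). Already-revised patients excluded (6.4). Comparison times: 2 and 5 years (12.2). Maximum 100 patients (12.1).

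**Assumed inputs.** Registry rate cumulative from surgery; entrants have the same later hazard as unrevised non-entrants; 5-year risk R5 of 1%, 3% or 5%; year-1 hazard m times the later hazard, with m = 0.5, 1 or 2; entry time e of 12 months, with 24 months as a late-entry scenario.

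**Direction.** Let F(t) be cumulative revision from surgery. A cohort unrevised at e estimates (F(t) − F(e)) / (1 − F(e)). For F(t) < 1 this is below F(t) whenever F(e) > 0.

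**Size.** The later hazard is h = −ln(1 − R5) / (4 + m). Then F(1) = 1 − exp(−mh) and F(2) = 1 − exp(−(m + 1)h).

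Worked case, R5 = 3%, m = 1, e = 12 months:

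- h = −ln(0.97)/5 = 0.00609; F(1) = 0.607%; F(2) = 1.211%.
- At 2 years: (1.211 − 0.607)/0.99393 = 0.607%, which is 0.50 of 1.211%.
- At 5 years: (3.000 − 0.607)/0.99393 = 2.407%, which is 0.80 of 3%.

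Share of the from-surgery risk shown by the Extension rate, 12-month entry (nearly the same for all three R5 values):

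| Year-1 hazard relative to later | 2 years | 5 years |
|---|---|---|
| Half | 0.67 | 0.89 |
| Equal | 0.50 | 0.80 |
| Double | 0.33 | 0.67 |

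With equal hazards, moving entry across the visit window (10 to 14 months) changes the shares to 0.58–0.42 at 2 years and 0.83–0.77 at 5 years.

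Revisions omitted per 100 operated patients, 100 × F(e):

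| Entry, year-1 hazard | R5 = 1% | R5 = 3% | R5 = 5% |
|---|---|---|---|
| 12 months, equal | 0.20 | 0.61 | 1.02 |
| 12 months, double | 0.33 | 1.01 | 1.70 |
| 24 months, equal | 0.40 | 1.21 | 2.03 |
| 24 months, double | 0.50 | 1.51 | 2.53 |

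**Against chance.** The binomial SD of the 5-year count in 100 patients is √(100 × R5 × (1 − R5)) = 0.99, 1.71 and 2.18. The omission is smaller than this in every cell except the last: 2.53 against 2.18. Even with no revisions in 100 patients, the exact 95% upper limit is 1 − 0.025^(1/100) = 3.6%.

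**When there is no bias.** If the registry figure is a rate per component-year and trial exposure is counted from entry, a constant hazard gives the same expected rate before and after entry.

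**The case against.** The strongest reply is that the bias depends on a registry definition the documents do not give. That stands. The mention of 2 and 5 years may simply say when the comparison is made, since 12.2 also schedules analyses after those visits. A reader might infer that the registry rate must be cumulative from surgery; the text does not settle it, so the bias is conditional.

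Nor does 12.2 say that Extension data alone will be used. An analyst could add main-study revisions without contradicting the wording. But the Extension is the only source named, and no section brings earlier revisions in.

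The direction also needs the equal-hazard assumption. Extension entry requires fresh consent, willingness to comply and a workable place of residence (5.0, 6.3, 6.4), so selection could push the rate either way.

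A reader might further infer that early revisions are lost to the trial. They are not: main-study adverse event CRFs and Study Completion Forms hold them, and 12.2 tabulates adverse events separately. It would also be too strong to say that no revision between main-study completion and Extension consent can be known. Section 19.2 has open events followed to resolution, and checking eligibility under 6.4 would reveal a revision in a patient who responds to the invitation. What holds is narrower: no section requires a new revision in a non-entrant, after 30 days post-completion, to be recorded.

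Finally, few events are expected and nothing is decided on this comparison. That limits the importance of the point but does not remove the mismatch.

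**Conclusion.** The point holds as a minor, conditional one. Followed as written, 12.2 sets a rate among patients unrevised at entry beside registry rates whose definition is not stated. If those are cumulative from surgery, and entrants and unrevised non-entrants share the same later hazard, the trial rate is biased low whenever a revision precedes entry. Under the assumed hazards with 12-month entry, it shows 0.33 to 0.67 of the 2-year risk and 0.67 to 0.89 of the 5-year risk. In absolute terms the omission is at most about 2.5 revisions per 100 patients across the scenarios doubling or equalising the year-1 hazard, and usually within chance variation.

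The documents do not support reading this as a flaw in the trial's main result. The 12-month Oxford Knee Score analysis and the comparison between randomised groups do not use this rate. Nor do they support calling 6.4 an error: the eligibility rule can stay, because the issue is which events 12.2 counts and from when.

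**What to change.** In 12.2, state the registry metric and its time origin. Then choose one of two routes.

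1. **Count from surgery.** Count first revisions from the date of surgery in all operated patients, combining main-study adverse event CRFs and Study Completion Forms with Extension data. Use observed time at risk: main-study follow-up, then delayed entry at Extension consent. If there is an interval in which nobody is under observation, a delayed-entry survival curve cannot recover the risk in it; report first revisions per observed component-year instead, against a registry rate on the same scale. Give a 95% confidence interval.
2. **Keep the Extension rate.** Label it as conditional on being unrevised at entry, and compare it with a registry rate conditional in the same way.

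Under either route, disclose that no section requires new revisions in non-entrants to be recorded once main-study follow-up ends (30 days post-completion).

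The cost is a few sentences in 12.2, with no new visits and no change to 6.4, because main-study revisions are already on forms. The downsides are that a from-surgery rate may look slightly less favourable, a component-year rate relies on a roughly constant hazard, and ascertainment in non-entrants may remain incomplete.
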